This document is confidential and the property of Stanford University School of Medicine.

8.3.1	Study Sponsor Notification by Investigator	11
8.3.2	EC/IRB Notification by Investigator	12
8.3.3	FDA Notification by Sponsor	12
8.4	UNBLINDING PROCEDURES.....	12
8.5	STOPPING RULES	ERROR! BOOKMARK NOT DEFINED.
8.6	MEDICAL MONITORING.....	12
8.6.1	Internal Data and Safety Monitoring Board	Error! Bookmark not defined.
8.6.2	Independent Data and Safety Monitoring Board	Error! Bookmark not defined.
9	DATA HANDLING AND RECORD KEEPING	12
9.1	CONFIDENTIALITY	12
9.2	SOURCE DOCUMENTS.....	13
9.3	CASE REPORT FORMS.....	13
9.4	RECORDS RETENTION.....	13
10	STUDY MONITORING, AUDITING, AND INSPECTING	13
10.1	STUDY MONITORING PLAN	13
10.2	AUDITING AND INSPECTING.....	14
11	ETHICAL CONSIDERATIONS	14
12	STUDY FINANCES	14
12.1	FUNDING SOURCE	14
12.2	CONFLICT OF INTEREST	15
12.3	SUBJECT STIPENDS OR PAYMENTS	ERROR! BOOKMARK NOT DEFINED.
13	PUBLICATION PLAN	15
14	REFERENCES	15
15	ATTACHMENTS	15

CONFIDENTIAL

This document is confidential and the property of Stanford University School of Medicine.

List of Abbreviations

ESQ – Esophageal symptoms questionnaire

NMDA - N-methyl-D-aspartate

POEM - Peroral endoscopic myotomy

SHC – Stanford Hospital & Clinics

CONFIDENTIAL

This document is confidential and the property of Stanford University School of Medicine.

Study Summary

Title	A prospective, randomized, double-blind, placebo-controlled trial of the effects of magnesium sulfate on postoperative esophageal spasm-associated pain following peroral endoscopic myotomy
Short Title	MgPOEM
Protocol Number	58859
Methodology	Randomized, double-blind, placebo-controlled prospective trial
Study Duration	2 years
Study Center(s)	Single-center
Objectives	This study hypothesizes that among patients having peroral endoscopic myotomy, intraoperative magnesium sulfate infusion will reduce the severity of postoperative pain while decreasing perioperative opioid requirements.
Number of Subjects	100
Diagnosis and Main Inclusion Criteria	Diagnosis: Esophageal motility disorder, including achalasia Main Inclusion Criteria: Patient undergoing peroral endoscopic myotomy
Study Product, Dose, Route, Regimen	Magnesium sulfate. 50 mg/kg (based on lean body weight) intravenous over 15 minutes at start of mucosal incision, followed by 25 mg/kg/hr infusion that is turned off at patient extubation

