3.3 Secondary Study Endpoints

This study will assess the efficacy of magnesium sulfate on decreasing intraoperative opioid usage, postoperative opioid consumption, discharge opioid prescription, and on decreasing postoperative pain as measured by the esophageal symptoms questionnaire score at 24 hours.

4 Subject Selection and Withdrawal

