7.2 Statistical Methods

Data will be expressed as means \pm SD, number (proportion), relative risk, 95% CI, absolute risk reduction, or number needed to treat.

The primary outcome is the incidence of esophageal spasm-related pain at 0 h postoperatively, compared using the chi-square test.

The secondary outcomes of the incidence of esophageal spasm-related pain at 24 hours postoperatively, intraoperative opioid usage, postoperative opioid consumption, and discharge opioid prescription will be compared using the chi-square test or Fisher's exact test as appropriate. Continuous variables will be compared using the Mann–Whitney *U* test. Categorical variables will be compared using the chi-square test or Fisher's exact test as appropriate.

Post hoc subgroup analyses will be conducted regarding the incidence of esophageal spasm-related pain according to achalasia type (e.g. type 1, 2, or 3), preoperative H2-receptor antagonist use, preoperative proton pump inhibitor use, and intraoperative opioid usage. *Post hoc* subgroup analysis will be further conducted on postoperative magnesium levels and the incidence of esophageal spasm-related pain at 24 hours.

All *P* values will be two-sided, and a value of $P < 0.05$ will be considered statistically significant.

Comparisons of postoperative pain between the two groups at time 0 h and time 24 h will be analyzed using the Mann–Whitney *U* test and performed using an adjusted significance level of 0.0125 (0.05/4) after *post hoc* analysis using the Bonferroni method.

Statistical analyses will be performed using R version 4.0.3.

CONFIDENTIAL

This document is confidential and the property of Stanford University School of Medicine.

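### The three opioid secondary outcomes are each tested at two-sided 0.05 with no gate, order, adjustment or exploratory label, so the chance of at least one false opioid-sparing claim is about 10–14%

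*Combined protocol and SAP*

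**What the plan says.** The Objectives row of the Study Summary states a two-part hypothesis: "intraoperative magnesium sulfate infusion will reduce the severity of postoperative pain while decreasing perioperative opioid requirements". Section 7.2 names one primary outcome, the incidence of spasm-related pain at 0 h, which addresses only the pain part.

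The opioid part appears among the secondaries. Section 3.3 words it as an efficacy aim: "This study will assess the efficacy of magnesium sulfate on decreasing intraoperative opioid usage, postoperative opioid consumption, discharge opioid prescription". Section 7.2 gives the tests: "intraoperative opioid usage, postoperative opioid consumption, and discharge opioid prescription will be compared using the chi-square test or Fisher's exact test as appropriate", with Mann–Whitney for continuous variables.

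Section 7.2 then gives two significance rules:
- The general rule: "All *P* values will be two-sided, and a value of $P < 0.05$ will be considered statistically significant".
- A special rule for "Comparisons of postoperative pain between the two groups at time 0 h and time 24 h", analysed by Mann–Whitney at an "adjusted significance level of 0.0125 (0.05/4) after *post hoc* analysis using the Bonferroni method".

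The list of secondaries is not the same throughout. Each list has four items:
- Section 7.2: 24 h pain incidence and the three opioid outcomes.
- Section 3.3: the three opioid outcomes and "decreasing postoperative pain as measured by the esophageal symptoms questionnaire score at 24 hours".
- Study Summary: intraoperative opioids, postoperative opioids, pain at 24 h and the ESQ results. Discharge prescription is absent.

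**The concern.** Half of the hypothesis rests on three outcomes, and a significant result on any one could be reported as opioid sparing. As written, the trial could miss its primary outcome and still report a significant opioid reduction at the full 0.05, with three chances to do so. The plan neither limits that nor warns the reader that these results are exploratory.

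The Bonferroni sentence shows that the authors saw a multiplicity problem for pain, but the opioid outcomes are outside it. What is at stake is the opioid-sparing conclusion. The primary comparison is not affected.

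**Working it through.** **Inputs.** Threshold 0.05, two-sided, for every P value (7.2). Three opioid outcomes (3.3 and 7.2). Adjusted level 0.0125 for pain comparisons at 0 h and 24 h (7.2). The documents give no correlations between outcomes, so 0, 0.5 and 0.8 are assumed to show a range. Each test is taken to have an actual size of 5%.

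**The plan's own figure.** 0.05/4 = 0.0125, so the arithmetic reproduces. The sentence names two comparisons, however, and two would give 0.05/2 = 0.025. The plan does not say which four tests the divisor counts.

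**Three opioid tests, no true effect on any.**
- Independent: 1 − 0.95³ = 1 − 0.8574 = 14.3%.
- Common correlation ρ: 1 − ∫ [Φ((1.96 − √ρ·u)/√(1−ρ)) − Φ((−1.96 − √ρ·u)/√(1−ρ))]³ φ(u) du. This gives 12.5% at ρ = 0.5 and 9.8% at ρ = 0.8. Simulations of 1,000,000 draws gave 12.6%, and 9.8% to 9.9%.

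**A narrower reading.** If discharge prescription is left out, as in the Study Summary, two opioid tests remain: 1 − 0.95² = 9.8% if independent and 9.1% at ρ = 0.5.

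**Does the 0.0125 rule change the picture?** It reaches no opioid outcome, so the three-test figures stand. The rates below are for the wider set of secondaries, by how far the rule is read to extend.

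| Tests counted | ρ = 0 | ρ = 0.5 | ρ = 0.8 |
|---|---|---|---|
| Three opioid tests at 0.05 | 14.3% | 12.5% | 9.8% |
| Plus 24 h pain at 0.0125 | 15.3% | 13.1% | 10.0% |
| Plus 24 h pain and 24 h ESQ, both at 0.0125 | 16.4% | 13.7% | 10.1% |
| Four secondaries, all at 0.05 | 18.5% | 15.6% | 11.4% |
| Five secondaries, all at 0.05 | 22.6% | 18.3% | 12.7% |

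For example, the second row at ρ = 0 is 1 − 0.95³ × 0.9875 = 15.3%. The last two rows apply only if the 0.0125 rule covers none of the pain secondaries, which the text does not settle.

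**After the fix.** Holm over three tests starts at 0.05/3 = 0.0167. With no true effect and independent tests, the chance of any rejection is 1 − (1 − 0.0167)³ = 4.9%. Holm keeps it at or below 5% whatever the correlation.

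**The case against.** The strongest reply has three parts.

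First, the plan never promises a 5% error rate across its secondaries. Its 0.05 is a rule for each test, and as such it holds. The plan names and powers one primary outcome, and calling the others secondary already ranks them lower. Many single-center trials leave secondaries unadjusted. This stands as far as it goes: the 10–14% does not breach a stated familywise guarantee. It does not settle the matter, because opioid reduction is in the hypothesis, the aims are worded as efficacy, and every P below 0.05 is to be called significant without qualification.

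Second, the plan does contain alpha control. A reader might infer that all four or five secondaries are tested at 0.05 with no control, and so quote 16–18% or more. The documents do not support that. Section 7.2 sets 0.0125 for pain comparisons at 0 h and 24 h, and section 3.3 describes the 24 h ESQ score as a measure of postoperative pain, so the rule may well cover it. Whether it covers the 24 h incidence, tested by chi-square or Fisher, is unclear, but unclear scope is not absence. The 16–18% also needs an assumed correlation near 0.5, and it mixes pain outcomes into a claim about opioids.

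Third, a reader might infer that a borderline opioid result, say P = 0.03, could never survive a controlled procedure. That is too strong. It would survive if placed first in a fixed sequence, or under Holm if the smaller P values had already been rejected. It fails Holm when it is the smallest of the three, because 0.03 exceeds 0.0167.

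**Conclusion.** The point holds for the three opioid outcomes. They are the only tests of the opioid hypothesis, and they are unadjusted, unordered, not gated on the primary and not labelled exploratory. With no true effect on any of them, the chance of at least one false opioid claim is about 10–14%.

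That range assumes correlations between 0 and 0.8 and tests of exact 5% size. A higher correlation would bring the rate closer to 5%, as would Fisher's exact test, which tends to be conservative.

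The 0.0125 rule is a separate defect of wording: two comparisons are named, the divisor is four, and the scope over 24 h pain incidence and 24 h ESQ is not stated. None of this touches the primary test or its sample size.

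**What to change.** Replace both the general 0.05 sentence and the 0.0125 paragraph in section 7.2 with one rule. If only the first were changed, the 0.0125 rule would still apply to the pain scores and would conflict with the new text. The rule should say:
- The 0 h incidence of spasm-related pain is the only confirmatory test, at two-sided 0.05.
- If it is significant, intraoperative usage, postoperative consumption and discharge prescription are tested by Holm at an overall two-sided 0.05.
- If it is not significant, the opioid results are reported as exploratory estimates with 95% CIs and no claim of significance.
- All other secondaries (24 h pain incidence, pain scores, 24 h ESQ) are reported in that exploratory way whatever the primary shows.

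A simpler alternative is to label every secondary exploratory and draw no confirmatory conclusion on opioid sparing.

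Either way, use one list of secondaries in the Study Summary, 3.3 and 7.2. Holm needs a fixed number of tests, so each opioid outcome should have one prespecified form.

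The cost is a short rewrite, with no extra patients or data. Under Holm the smallest opioid P value must be below 0.0167, and no opioid claim is possible if the primary fails. The primary test and its power are unchanged.

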7.3 Subject Population(s) for Analysis

Enrollment will cease when the target sample size is obtained. Analyses will be performed on an intention-to-treat basis. All patients who are enrolled and randomly allocated for treatment will be included in the analysis.

8 Safety and Adverse Events

8.1 Definitions

Adverse Event

An **adverse event** (AE) is any symptom, sign, illness or experience that develops or worsens in severity during the course of the study. Intercurrent illnesses or injuries should be regarded as adverse events. Abnormal results of diagnostic procedures are considered to be adverse events if the abnormality:

- results in study withdrawal
- is associated with a serious adverse event
- is associated with clinical signs or symptoms
- leads to additional treatment or to further diagnostic tests
- is considered by the investigator to be of clinical significance

Serious Adverse Event

Adverse events are classified as serious or non-serious. A **serious adverse event** is any AE that is:

- fatal
- life-threatening
- requires or prolongs hospital stay
- results in persistent or significant disability or incapacity
- a congenital anomaly or birth defect
- an important medical event

Important medical events are those that may not be immediately life threatening, but are clearly of major clinical significance. They may jeopardize the subject, and may require intervention to prevent one of the other serious outcomes noted above. For example, drug overdose or abuse, a seizure that did not result in in-patient hospitalization, or intensive treatment of bronchospasm in an emergency department would typically be considered serious.

All adverse events that do not meet any of the criteria for serious should be regarded as **non-serious adverse events**.

Adverse Event Reporting Period

The study period during which adverse events must be reported is normally defined as the period from the initiation of any study procedures to the end of the study treatment follow-up. For this study, the study treatment follow-up is defined as 30 days following the last administration of study treatment.

Preexisting Condition

CONFIDENTIAL

This document is confidential and the property of Stanford University School of Medicine.

A preexisting condition is one that is present at the start of the study. A preexisting condition should be recorded as an adverse event if the frequency, intensity, or the character of the condition worsens during the study period.

General Physical Examination Findings

At screening, any clinically significant abnormality should be recorded as a preexisting condition. At the end of the study, any new clinically significant findings/abnormalities that meet the definition of an adverse event must also be recorded and documented as an adverse event.

Post-study Adverse Event

All unresolved adverse events should be followed by the investigator until the events are resolved, the subject is lost to follow-up, or the adverse event is otherwise explained. At the last scheduled visit, the investigator should instruct each subject to report any subsequent event(s) that the subject, or the subject's personal physician, believes might reasonably be related to participation in this study. The investigator should notify the study sponsor of any death or adverse event occurring at any time after a subject has discontinued or terminated study participation that may reasonably be related to this study. The sponsor should also be notified if the investigator should become aware of the development of cancer or of a congenital anomaly in a subsequently conceived offspring of a subject that has participated in this study.

Abnormal Laboratory Values

A clinical laboratory abnormality should be documented as an adverse event if any one of the following conditions is met:

- The laboratory abnormality is not otherwise refuted by a repeat test to confirm the abnormality
- The abnormality suggests a disease and/or organ toxicity
- The abnormality is of a degree that requires active management; e.g. change of dose, discontinuation of the drug, more frequent follow-up assessments, further diagnostic investigation, etc.

Hospitalization, Prolonged Hospitalization or Surgery

Any adverse event that results in hospitalization or prolonged hospitalization should be documented and reported as a serious adverse event unless specifically instructed otherwise in this protocol. Any condition responsible for surgery should be documented as an adverse event if the condition meets the criteria for an adverse event.

Neither the condition, hospitalization, prolonged hospitalization, nor surgery are reported as an adverse event in the following circumstances:

- Hospitalization or prolonged hospitalization for diagnostic or elective surgical procedures for a preexisting condition. Surgery should **not** be reported as an outcome of an adverse event if the purpose of the surgery was elective or diagnostic and the outcome was uneventful.
- Hospitalization or prolonged hospitalization required to allow efficacy measurement for the study.

CONFIDENTIAL

This document is confidential and the property of Stanford University School of Medicine.

- Hospitalization or prolonged hospitalization for therapy of the target disease of the study, unless it is a worsening or increase in frequency of hospital admissions as judged by the clinical investigator.

8.2 Recording of Adverse Events

At each contact with the subject, the investigator must seek information on adverse events by specific questioning and, as appropriate, by examination. Information on all adverse events should be recorded immediately in the source document, and also in the appropriate adverse event module of the case report form (CRF). All clearly related signs, symptoms, and abnormal diagnostic procedures results should be recorded in the source document, though should be grouped under one diagnosis.

All adverse events occurring during the study period must be recorded. The clinical course of each event should be followed until resolution, stabilization, or until it has been determined that the study treatment or participation is not the cause. Serious adverse events that are still ongoing at the end of the study period must be followed up to determine the final outcome. Any serious adverse event that occurs after the study period and is considered to be possibly related to the study treatment or study participation should be recorded and reported immediately.

8.3 Reporting of Serious Adverse Events

8.3.1 Study Sponsor Notification by Investigator

A serious adverse event must be reported to the study sponsor by telephone within 24 hours of the event. A Serious Adverse Event (SAE) form must be completed by the investigator and faxed to the study sponsor within 24 hours. The investigator will keep a copy of this SAE form on file at the study site. Report serious adverse events by phone and secure email to:

[name]

[contact]

[contact]

At the time of the initial report, the following information should be provided:

- Study identifier
- Study Center
- Subject number
- A description of the event
- Date of onset
- Current status
- Whether study treatment was discontinued
- The reason why the event is classified as serious
- Investigator assessment of the association between the event and study treatment

Within the following 48 hours, the investigator must provide further information on the serious adverse event in the form of a written narrative. This should include a copy of the completed Serious Adverse Event form, and any other diagnostic information that will assist the understanding of the event. Significant new information on ongoing serious adverse events should be provided promptly to the study sponsor

CONFIDENTIAL

This document is confidential and the property of Stanford University School of Medicine.

8.3.2 EC/IRB Notification by Investigator

Reports of all serious adverse events (including follow-up information) must be submitted to the EC/IRB within 10 working days. Copies of each report and documentation of EC/IRB notification and receipt will be kept in the Clinical Investigator's binder.

8.3.3 FDA Notification by Sponsor

The study sponsor shall notify the FDA by telephone or by facsimile transmission of any unexpected fatal or life-threatening experience associated with the use of the drug as soon as possible but no later than 7 calendar days from the sponsor's original receipt of the information. Other serious, unexpected adverse events associated with the use of study drug shall be reported to the FDA no later than 15 calendar days from the sponsors' original receipt of the information.

If a previous adverse event that was not initially deemed reportable is later found to fit the criteria for reporting, the study sponsor will submit the adverse event in a written report to the FDA as soon as possible, but no later than 15 calendar days from the time the determination is made.

8.4 Unblinding Procedures

Postoperative magnesium levels evaluated after surgery will reveal those among study participants who received magnesium or normal saline. If a study participant experiences a serious adverse event postoperatively, including cardiorespiratory arrest, unblinding will occur to ensure the patient's safety by evaluating if the patient would benefit from administration of calcium chloride therapy. The patient's randomization envelope contents will be shared with the care team. Documentation of this will be indicated in our data collection spreadsheets. The sponsor will be notified of each participant who was unblinded within 24 hours by phone or email, followed by a written narrative of the event within 48 hours.

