4.4.2 Data Collection and Follow-up for Withdrawn Subjects

All data will be de-identified and stored in Stanford-secured encrypted devices, only accessible to research personnel. For withdrawn subjects, we will attempt to seek permission for magnesium levels drawn during the defined follow-up period (postoperative days 0 and 1). This is related to the safety profile of the study drug. Otherwise, all other data related to the withdrawn subject will be destroyed, and no further follow-up information will be collected.

5 Study Drug

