5.8 Blinding of Study Drug

The study drug will be blinded to the endoscopist and patient. While the study or control drug is being prepared by the anesthesia team, the endoscopist will not be present in the operating room environment. The 20 ml syringe in which the drug is prepared will be labeled as "study" for the purpose of minimizing drug error during the course of intraoperative management.

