6.2 Day of surgery

- 6.2.1 In the preoperative holding area, all enrolled patients will have preoperative plasma calcium and magnesium levels drawn and complete the esophageal symptoms questionnaire (ESQ), a validated survey to assess symptoms of dysphagia, globus, and reflux.

6.2.2 The patient will proceed to the OR for anesthetic care.

- 6.2.2.1 Patients will undergo rapid sequence induction of general anesthesia. In the control group, the anesthesia team will use ketamine, propofol, succinylcholine, and esmolol and/or opioids at their discretion. In the treatment arm, the anesthesia team will use ketamine and propofol using lean body weight (LBW) dosing, and succinylcholine at total body weight (TBW) dosing. After endotracheal tube placement and confirmation, sevoflurane in air and oxygen will be used for maintenance of general anesthesia. The anesthesiologist will ensure adequate neuromuscular relaxation throughout the case.

- 6.2.2.2 In the treatment arm, the anesthesia team will prepare a magnesium sulfate infusion within a 20 ml syringe. Patients will receive a magnesium sulfate bolus of 50 mg/kg lean body weight over 15 minutes, followed by a magnesium sulfate infusion at 25 mg/kg/hr when the endoscopist begins mucosal incision. In addition, the patients will receive dexamethasone 0.1-0.2 mg/kg at the start of case, and ondansetron 4 mg at the end of case. The magnesium infusion will be discontinued at extubation. After surgery, patients will be admitted to the postanesthesia care unit. For mild pain reported as a numeric score ranging from 1 to 3, acetaminophen 1000 mg IV will be offered. For pain greater than a score of 3, opioids (fentanyl and hydromorphone) will be available. For nausea and vomiting, prochlorperazine and haloperidol will be provided. Calcium gluconate and a code cart with emergency drugs and airway equipment will be made available in case of symptoms concerning for magnesium toxicity.

- 6.2.2.3 In the control arm, the anesthesia team will prepare a normal saline infusion within a 20 ml syringe. Patients will receive a normal saline bolus of 50 mg/kg lean body weight over 15 minutes, followed by a normal saline infusion at 25 mg/kg/hr when the endoscopist begins mucosal incision. Opioids (fentanyl and hydromorphone) will be administered for analgesia at the discretion of the anesthesia team. In addition, patients

CONFIDENTIAL

This document is confidential and the property of Stanford University School of Medicine.

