will receive dexamethasone and ondansetron in the aforementioned doses. After surgery, patients will be admitted to the postanesthesia care unit, where opioids (fentanyl and hydromorphone) and antiemetics (anesthesia team's discretion) will be available for further pain and nausea management.

6.3 All study participants will repeat the ESQ in the PACU when the nursing team deems the patient's recovery appropriate enough to participate.

6.4 Postoperative Day 1

6.4.1 The ESQ and serum calcium/magnesium levels will be reobtained in the morning of POD1.

7 Statistical Plan

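### The POD1 magnesium result, which the protocol says reveals the arm, is neither masked nor ordered after the POD1 ESQ, so the 24-hour secondary outcomes can be recorded unblinded

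*Combined protocol and SAP*

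**What the plan says.** Section 5.8 defines the blind: "The study drug will be blinded to the endoscopist and patient". It names no blinded outcome assessor or data collector.

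Section 8.4 concedes that a laboratory value breaks this blind: "Postoperative magnesium levels evaluated after surgery will reveal those among study participants who received magnesium or normal saline". The rest of 8.4 deals with unblinding after a serious adverse event. It does not say who may see magnesium results in routine care.

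Section 6.4.1 sets the POD1 procedures in one sentence: "The ESQ and serum calcium/magnesium levels will be reobtained in the morning of POD1". The only other draw in the procedures is preoperative; under 6.2.1, "all enrolled patients will have preoperative plasma calcium and magnesium levels drawn and complete the esophageal symptoms questionnaire (ESQ").

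The 24-hour data are used as secondary outcomes. Section 3.3 lists "decreasing postoperative pain as measured by the esophageal symptoms questionnaire score at 24 hours", and section 7.2 lists the "secondary outcomes of the incidence of esophageal spasm-related pain at 24 hours postoperatively". Section 7.2 also plans a Mann–Whitney comparison of pain at 0 h and 24 h at a level of 0.0125, and an analysis relating postoperative magnesium levels to 24-hour pain.

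The primary outcome is earlier: "The primary outcome is the incidence of esophageal spasm-related pain at 0 h postoperatively, compared using the chi-square test".

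**The concern.** The protocol itself says that the test reveals the arm, schedules it alongside a subjective outcome, and places no barrier between the two. Both parties whom 5.8 declares blinded could learn the assignment from a routine study procedure before the ESQ is answered. The person collecting the ESQ could learn it the same way.

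The ESQ and pain scores are self-reported. A patient who knows the arm may answer differently, and a collector who knows it may ask differently. No analysis can remove such a bias afterwards, so it has to be prevented at collection. At stake is whether the double-blind label can be relied on for the 24-hour results. The planned analysis of magnesium level against 24-hour pain is exposed in the same way.

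**Working it through.** **Comparing the sections**

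1. Does the level reveal the arm? Section 8.4 says so. How well a POD1 level separates the arms cannot be checked from the documents, so this step rests on the protocol's own statement.
2. Which level is meant? Section 8.4 names no day. Section 6.4.1 schedules the only postoperative draw, so POD1 is the natural reading. Section 4.4.2, however, mentions "magnesium levels drawn during the defined follow-up period (postoperative days 0 and 1"), and the procedures schedule no postoperative draw on day 0.
3. Does that draw coincide with the outcome? Yes. Section 6.4.1 puts both on the POD1 morning, and this is the only ESQ after the PACU one, so it must supply the 24-hour score.
4. Is there an order or a mask? None was found in 5.8, 6.4.1, 7.2 or 8.4, or elsewhere.
5. Is the primary outcome exposed? Not by the schedule as written, because 0 h comes before the POD1 level.

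**Illustration of size**

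The plan has no figure to reproduce here. The inputs are:

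- From the plan: 50 patients per arm (7.1), the chi-square test (7.2), and significance levels of 0.05 and 0.05/4 = 0.0125 (7.2).
- Assumed: the same true 24-hour rate in both arms (40%, with 30% and 60% as a range), and an average reduction in reported incidence of 0, 2.5, 5 or 10 points in the magnesium arm. If half the arm were influenced by 5 points each, the average would be 0.5 × 5 = 2.5 points.

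Let x₀ and x₁ be the numbers reporting pain in the two arms, n = 50 and p̄ = (x₀ + x₁)/(2n). The uncorrected statistic is

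T = [(x₀ − x₁)/n]² / [2p̄(1 − p̄)/n].

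The test rejects when T exceeds 3.84 (level 0.05) or 6.24 (level 0.0125). The rejection probability is the sum of Bin(x₀; 50, p) × Bin(x₁; 50, p − shift) over all pairs that reject.

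| Assumed rate | Level | No shift | 2.5 points | 5 points | 10 points |
|---|---|---|---|---|---|
| 40% | 0.05 | 5.2% | 5.9% | 8.2% | 18.0% |
| 40% | 0.0125 | 1.2% | 1.5% | 2.5% | 7.5% |
| 30% | 0.05 | 5.0% | 5.9% | 8.7% | 21.2% |
| 60% | 0.05 | 5.2% | 6.1% | 8.5% | 18.4% |

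The rows at 0.05 correspond to the 24-hour incidence test. The row at 0.0125 is only a rough guide to the stricter comparison, because the plan uses Mann–Whitney there and that test is not modelled. The ESQ score as a continuous endpoint is not modelled either.

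**The case against.** The strongest reply is that unblinding is possible but not shown. The result reveals the arm, not the drawing of blood. Section 6.4.1 does not say that the result is back, or shown to anyone, before the ESQ is answered. Because the patient completes the ESQ, bias also requires that the patient, or someone influencing the patient, learns the result first. This stands, and it limits the point to a risk the plan leaves open. It does not remove the point, because the plan requires neither safeguard that would close it.

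A second reply is that the effect may be negligible. This also stands in part: an average shift of 2.5 points barely moves the error rate, and no source in the documents supports a larger one.

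A third is that the magnesium level is not the only route. The anesthesia team prepares the drug (5.4), and research staff review the anesthesia medication record (5.5). Neither group is declared blinded, so staff may know the arm before any POD1 blood is drawn. This is correct. It does not excuse opening a further route to the patient and endoscopist, but it means that masking the laboratory result alone would be an incomplete repair.

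A reader might also infer that any bias must favour magnesium. Nothing in the documents establishes a direction, and patients who learn either assignment could report either way. Nor do the documents support the inference that the primary result is compromised: the day-0 reference in 4.4.2 has no matching postoperative draw in the procedures.

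**Conclusion.** The point holds as a modest, inexpensive improvement confined to the 24-hour secondary outcomes. The plan names a test that reveals the arm, takes it on the same morning as a self-reported outcome, and neither orders the two nor masks the result.

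This rests on two readings: that 8.4 refers to the POD1 level, and that the POD1 ESQ is the 24-hour assessment. Both are the natural reading of the schedule. The 0 h primary outcome is unaffected unless a postoperative day-0 level is in fact drawn and seen before the PACU assessment.

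The size and direction of any bias are unknown. At an assumed 40% rate, the illustration runs from almost no inflation at a 2.5-point average shift to 18.0% at 10 points (7.5% at the 0.0125 level). These figures show sensitivity to assumed shifts and are not an estimate for this trial. The documents do not support saying that the 24-hour outcome will be collected unblinded, only that it can be.

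**What to change.** - **Order and masking (6.4.1).** Require the POD1 pain score and ESQ to be completed and recorded before the POD1 blood is drawn. Failing that, require this before the magnesium result is released to the patient, the endoscopist or the ESQ collector. State an explicit exception for release on safety grounds, and leave 8.4 otherwise unchanged.
- **Collector.** Have the ESQ collected by existing staff who have not seen the magnesium results, the randomization envelope or the anesthesia drug record reviewed under 5.5.
- **Day-0 level.** Reconcile the day-0 level mentioned in 4.4.2 with the schedule in section 6. If a postoperative level is drawn that day, apply the same masking relative to the PACU assessment.

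The questionnaire, blood test and sample size stay the same. The cost is protocol wording, a small scheduling constraint on the POD1 morning, and some care in allocating existing staff.
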